6.2.2.2 Summary of Response Measures

- i. Primary response measures
  - 1. Skin (BSA), erythema, moveable, non-moveable
  - 2. Eyes (Schirmer)
  - 3. Mouth (modified OMRS)
  - 4. Liver (bilirubin, AST, ALT)
  - 5. GI tract (GI response scale)

- 6. Lung (FEV, DLCO, LFS)
- 7. Clinician assessment scale (3-point, 7-point change, 11-point global)
- 8. ROM visual Carpenter scale (1-7 and 1-4)
- 9. NIH organ scoring
- ii. Secondary assessments
  - 1. Platelet count, CRP, C3, C4, albumen
  - 2. 2 and 6 minute walk time
  - 3. Grip strength
  - 4. Lee symptom scale
  - 5. HAP, SF-36, Karnofsky
  - 6. MRI (if positive baseline)
  - 7. Disabilities of the Arm Hand and Shoulder (DASH)
- 6.2.2.3 Other endpoints to be recorded at the evaluation time points: Need for secondary systemic therapy for GvHD, malignancy progression, discontinuation of immune suppression, steroid doses, other immunosuppressive drug doses, intensity of immunosuppression, NIH global severity (Appendix P), survival, progression-free/malignancy-free survival, disability-free survival.

#### 6.3 TOXICITY CRITERIA

The following adverse event management guidelines are intended to ensure the safety of each patient while on the study. The descriptions and grading scales found in the revised NCI Common Terminology Criteria for Adverse Events (CTCAE) version 4.0 will be utilized for AE reporting. All appropriate treatment areas should have access to a copy of the CTCAE version 4.0. A copy of the CTCAE version 4.0 can be downloaded from the CTEP web site: (http://ctep.cancer.gov/protocolDevelopment/electronic\_applications/ctc.htm#ctc\_40).

#### 7 NIH REPORTING REQUIREMENTS/DATA AND SAFETY MONITORING PLAN

#### 7.1 **DEFINITIONS**

Please refer to definitions provided in Policy 801: Reporting Research Events found at: https://irbo.nih.gov/confluence/pages/viewpage.action?pageId=36241835#Policies&Guidance-800Series-ComplianceandResearchEventReportingRequirements.

# 7.2 OHSRP OFFICE OF COMPLIANCE AND TRAINING / IRB REPORTING

#### 7.2.1 Expedited Reporting

Please refer to the reporting requirements in Policy 801: Reporting Research Events and Policy 802 Non-Compliance Human Subjects Research found at: https://irbo.nih.gov/confluence/pages/viewpage.action?pageId=36241835#Policies&Guidance-800Series-ComplianceandResearchEventReportingRequirements.. Note: Only IND Safety Reports that meet the definition of an unanticipated problem will need to be reported per these policies.

### 7.2.2 IRB Requirements for PI Reporting at Continuing Review

Please refer to the reporting requirements in Policy 801: Reporting Research Events found at: https://irbo.nih.gov/confluence/pages/viewpage.action?pageId=36241835#Policies&Guidance-800Series-ComplianceandResearchEventReportingRequirements..

### 7.3 NCI CLINICAL DIRECTOR REPORTING

Problems expeditiously reviewed by the OHSRP in the NIH eIRB system will also be reported to the NCI Clinical Director/designee; therefore, a separate submission for these reports is not necessary.

In addition to those reports, all deaths that occur within 30 days after receiving a research intervention should be reported via email unless they are due to progressive disease.

To report these deaths, please send an email describing the circumstances of the death to [contact] within one business day of learning of the death.

#### 7.4 NIH REQUIRED DATA AND SAFETY MONITORING PLAN

Serious adverse events potentially attributable to the study medication or procedures will be reported to IRB. If trends are noted and/or risks warrant it, accrual will be interrupted and/or the protocol and/or consent document will be amended accordingly.

#### 7.4.1 Principal Investigator/Research Team

The clinical research team will meet on a regular weekly basis when participants are being actively treated on the trial to discuss each participant. Decisions about dose level enrollment and dose escalation if applicable will be made based on the toxicity data from prior participants.

All data will be collected in a timely manner and reviewed by the principal investigator or a lead associate investigator. Events meeting requirements for expedited reporting as described in section 7.2.1 will be submitted within the appropriate timelines.

The principal investigator will review adverse event and response data on each participant to ensure safety and data accuracy. The principal investigator will personally conduct or supervise the investigation and provide appropriate delegation of responsibilities to other members of the research staff.

# 8 SPONSOR PROTOCOL/SAFETY REPORTING

#### 8.1 **DEFINITIONS**

#### 8.1.1 Adverse Event

Any untoward medical occurrence in a patient or clinical investigation subject administered a pharmaceutical product and which does not necessarily have a causal relationship with this treatment. An adverse event (AE) can therefore be any unfavorable and unintended sign (including an abnormal laboratory finding), symptom, or disease temporally associated with the use of a medicinal (investigational) product, whether or not related to the medicinal (investigational) product (ICH E6 (R2))

#### 8.1.2 Serious Adverse Event (SAE)

An adverse event or suspected adverse reaction is considered serious if in the view of the investigator or the sponsor, it results in any of the following:

- Death,
- A life-threatening adverse event (see section 8.1.3)
- Inpatient hospitalization or prolongation of existing hospitalization
  - A hospitalization/admission that is pre-planned (i.e., elective or scheduled surgery arranged prior to the start of the study), a planned hospitalization for pre-existing condition, or a procedure required by the protocol, without a serious deterioration in health, is not considered a serious adverse event.
  - A hospitalization/admission that is solely driven by non-medical reasons (e.g., hospitalization for patient or subject convenience) is not considered a serious adverse event.
  - Emergency room visits or stays in observation units that do not result in admission to the hospital would not be considered a serious adverse event. The reason for seeking medical care should be evaluated for meeting one of the other serious criteria.
- Persistent or significant incapacity or substantial disruption of the ability to conduct normal life functions
- A congenital anomaly/birth defect
- Important medical events that may not result in death, be life-threatening, or require hospitalization may be considered a serious adverse drug experience when, based upon appropriate medical judgment, they may jeopardize the patient or subject and may require medical or surgical intervention to prevent one of the outcomes listed in this definition.

#### 8.1.3 Life-threatening

An adverse event or suspected adverse reaction is considered "life-threatening" if, in the view of either the investigator or sponsor, its occurrence places the patient or subject at immediate risk of death. It does not include an adverse event or suspected adverse reaction that, had it occurred in a more severe form, might have caused death. (21CFR312.32)

## 8.1.4 Severity

The severity of each Adverse Event will be assessed utilizing the CTCAE version 4.0.

8.1.5 Relationship to Study Product

All AEs will have their relationship to study product assessed using the terms: related or not related.

- Related There is a reasonable possibility that the study product caused the adverse event. Reasonable possibility means that there is evidence to suggest a causal relationship between the study product and the adverse event.
- Not Related There is not a reasonable possibility that the administration of the study product caused the event.

# 8.2 Assessment of Safety Events

AE information collected will include event description, date of onset, assessment of severity and relationship to study product and alternate etiology (if not related to study product), date of resolution of the event, seriousness and outcome. The assessment of severity and relationship to the study product will be done only by those with the training and authority to make a diagnosis and listed on the Form FDA 1572 as the site principal investigator or sub-investigator. AEs occurring during the collection and reporting period will be documented appropriately regardless of relationship. AEs will be followed through resolution.

SAEs will be:

- Assessed for severity and relationship to study product and alternate etiology (if not related to study product) by a licensed study physician listed on the Form FDA 1572 as the site principal investigator or sub-investigator.
- Recorded on the appropriate SAE report form, the medical record and captured in the clinical database.
- Followed through resolution by a licensed study physician listed on the Form FDA 1572 as the site principal investigator or sub-investigator.

For timeframe of recording adverse events, please refer to section **Error! Reference source not found.**. All serious adverse events recorded from the time of first investigational product administration must be reported to the sponsor.

# 8.3 REPORTING OF SERIOUS ADVERSE EVENTS

Any AE that meets protocol-defined serious criteria or meets the definition of Adverse Event of Special Interest that require expedited reporting must be submitted immediately (within 24 hours of awareness) to OSRO Safety using the CCR SAE report form.

All SAE reporting must include the elements described in section 8.2.

SAE reports will be submitted to the Center for Cancer Research (CCR) at: [contact] and to the CCR PI and study coordinator. CCR SAE report form

and instructions can be found at: https://nih.sharepoint.com/:u:/r/sites/NCI-CCR-OCD-Communications/SitePages/Forms-and-Instructions.aspx?csf=1&web=1&e=uWBXtI

Following the assessment of the SAE by OSRO, other supporting documentation of the event may be requested by the OSRO Safety and should be provided as soon as possible.

# 8.4 SAFETY REPORTING CRITERIA TO THE PHARMACEUTICAL COLLABORATORS

Reporting will be per the collaborative agreement.

# 8.5 **Reporting Pregnancy**

All required pregnancy reports/follow-up to OSRO will be submitted to: [contact] and to the CCR PI and study coordinator. Forms and instructions can be found here: https://nih.sharepoint.com/:u:/r/sites/NCI-CCR-OCD- Communications/SitePages/Forms-and-Instructions.aspx?csf=1&web=1&e=uWBXtI

# 8.5.1 Maternal exposure

If a participant becomes pregnant during the course of the study, the study treatment should be discontinued immediately, and the pregnancy reported to the Sponsor no later than 24 hours of when the Investigator becomes aware of it. The Investigator should notify the Sponsor no later than 24 hours of when the outcome of the Pregnancy becomes known.

Pregnancy itself is not regarded as an SAE. However, congenital abnormalities or birth defects and spontaneous miscarriages that meet serious criteria (section **8.1.2**) should be reported as SAEs.

The outcome of all pregnancies occurring from the first dose of study therapy until 28 days after the last dose of study therapy should be followed up and documented.

# 8.5.2 Paternal exposure

Male participants should refrain from fathering a child or donating sperm during the study and for 28 days after the last dose of Pomalidomide.

Pregnancy of the participant's partner is not considered to be an AE. However, the outcome of all pregnancies occurring from the date of the first dose until 28 days after the last dose should, if possible, be followed up and documented. Pregnant partners may be offered the opportunity to participate in an institutional pregnancy registry protocol (e.g., the NIH IRP pregnancy registry study) to provide data about the outcome of the pregnancy for safety reporting purposes.

# 8.6 REGULATORY REPORTING FOR STUDIES CONDUCTED UNDER CCR-SPONSORED IND

Following notification from the investigator, CCR, the IND sponsor, will report any suspected adverse reaction that is both serious and unexpected. CCR will report an AE as a suspected adverse reaction only if there is evidence to suggest a causal relationship between the study product and the adverse event. CCR will notify FDA and all participating investigators (i.e., all investigators to whom the sponsor is providing drug under its INDs or under any investigator's IND) in an IND safety report of potential serious risks from clinical trials or any other source, as soon as possible, in accordance to 21 CFR Part 312.32.

All serious events will be reported to the FDA at least annually in a summary format.

## 8.7 SPONSOR PROTOCOL DEVIATION REPORTING

A Protocol Deviation is defined as any non-compliance with the clinical trial Protocol, Manual of Operational Procedures (MOP) and other Sponsor approved study related documents, GCP, or protocol-specific procedural requirements on the part of the participant, the Investigator, or the study site staff inclusive of site personnel performing procedures or providing services in support of the clinical trial.

It is the responsibility of the study Staff to document any protocol deviation identified by the Staff or the site Monitor in the CCR Protocol Deviation Tracking System (PDTS) online application. The entries into the PDTS online application should be timely, complete, and maintained per CCR PDTS user requirements.

In addition, any deviation to the protocol should be documented in the participant's source records and reported to the reviewing IRB per their guidelines. OSRO required protocol deviation reporting is consistent with E6(R2) GCP: Integrated Addendum to ICH E6(R1): 4.5 Compliance with Protocol; 5.18.3 (a), and 5.20 Noncompliance; and ICH E3 16.2.2 Protocol deviations.

# 9 CLINICAL MONITORING

As a sponsor for clinical trials, FDA regulations require the CCR to maintain a monitoring program. The CCR's program allows for confirmation of: study data, specifically data that could affect the interpretation of primary and secondary study endpoints; adherence to the protocol, regulations, ICH E6, and SOPs; and human subjects protection. This is done through independent verification of study data with source documentation focusing on:

- Informed consent process
- Eligibility confirmation
- Drug administration and accountability
- Adverse events monitoring
- Response assessment.

The monitoring program also extends to multi-site research when the CCR is the coordinating center.

This trial will be monitored by personnel employed by a CCR contractor. Monitors are qualified by training and experience to monitor the progress of clinical trials. Personnel monitoring this study will not be affiliated in any way with the trial conduct.

# **10 STATISTICAL CONSIDERATIONS**

It is known from prior trials that the pomalidomide MTD is about 3 mg/d in persons with bone marrow disorders receiving therapies for cancer. Due to high frequency of pomalidomide dose de-escalation observed in preliminary cGvHD experiences when given at 3 mg/d, this study will explore clinical toxicity of gradual escalation doses below 3.0 mg.

The primary objective of this study is to determine if patients with cGVHD will experience an acceptable level of clinical response when treated with either a constant low dose of pomalidomide (0.5 mg/day) for six months or a strategy of increasing dose of pomalidomide from 0.5 mg/d up through each individual patients' maximum tolerated dose, with escalations by

0.5 mg/d every 2 weeks to a maximum of 2.0 mg/d. The study will thus randomize patients between fixed low dose and escalating dose to tolerance, and will be considered a randomized phase II trial with a selection design component.

In each of the two arms, the trial will be conducted using a single stage design. With 16 patients on each arm, an exact binomial test would have 90% power to detect a difference between a 5% response rate and a 30% response rate using a 0.10 one-sided significance level and an exact binomial test. In addition, after the trial has ended, the 80% and 95% confidence limits will be determined for each arm about the observed response proportion in order to aid in interpretation of the results. If there are 3 or more responses in 16 patients, this would be sufficient to rule out a 5% response rate and demonstrate consistency with 30% or better response rates.

At the conclusion of the study, if both arms are able to accrue to the full 16 patients, the arm with the greater number of responses will be selected for further investigation subsequently. That is, if the fixed, low-dose arm, or the increasing dose level arm, has the greater number of responses, then that arm would be studied further. In the event of a tie, the lower dose arm would likely be preferred. As an example, if the true probabilities of response on the two arms were 0.10 and 0.30, then the probability of correctly selecting the superior arm would be 93%, and if the true probabilities on the two arms were 0.15 and 0.30, the probability of correct selection would be 84%.

As an early stopping rule for futility, if after 7 patients have enrolled on either arm, 0 have responded, then no further patients will be accrued to that arm as soon as this can be determined. In practice, this means that patients may continue to be accrued beyond 7 in an arm, but no more patients would be registered and treated on that arm once the first 7 were evaluated and no PRs or CRs were identified in those first 7.

To protect patient safety, an early stopping rule will be implemented as follows. For patients treated on either arm, if 2 patients in the first 6, or 33% of the patients at any time experience a DLT at a given dose level, no further patients will be treated at that given level on the trial. Furthermore, when more than 6 patients have received a given dose level, if at any time 33% or more patients experience a DLT when treated at that dose level, then no further patients will be treated at that dose level. Thus, as an example, should there be 2 patients with a DLT in the first 6 who are able to receive 2.0 mg/day on the dose escalating arm, then subsequent patients treated on that arm will not be escalated beyond 1.5 mg/day.

With two arms, each of which has a maximal accrual of 16 patients, up to 32 evaluable patients will be randomized. In order to allow for a very small number of patients who are not able to be evaluated at all for response, the accrual ceiling will be set at 35.

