## **3 STUDY IMPLEMENTATION**

#### 3.1 STUDY DESIGN

The study is a randomized phase 2 trial with the single stage selection design. It is known from prior trials that the maximum tolerated dose of pomalidomide is about 3 mg/d in persons with bone marrow disorders receiving prior therapies for cancer, in cGvHD doses <3mg/d have been well tolerated. This study will explore clinical toxicity of gradual escalation of pomalidomide doses <3 mg/d in subjects with cGvHD. Patients will receive either a constant low dose of pomalidomide (0.5 mg/day) for six months or a strategy of increasing dose of pomalidomide from 0.5 mg/d up through each individual patients' maximum tolerated dose, with escalations by 0.5 mg/d every 2 weeks to a maximum of 2.0 mg/d. In each of the two arms, the trial will use a single stage design.

As an early stopping rule for futility as outlined in section **8**, if after 7 patients have enrolled on either arm, 0 have responded, then no further patients will be accrued to that arm as soon as this can be determined. To protect patient safety, an early stopping rule will be implemented. With two arms, each of which has a maximal accrual of 16 patients, up to 32 evaluable patients will be randomized. Safety assessments and pregnancy testing for FCBP will be performed at scheduled intervals as described in the Study Calendar.

Response will be assessed every 3 months while taking pomalidomide following the criteria in Section 6.2. The primary efficacy endpoint will be evaluated at 6 months. Efficacy outcome is defined as clinical response (CR or PR) in subjects who enter the study with stable cGvHD or stable disease for  $\geq$ 3 mo for subjects with progressive cGvHD at study-entry. (Stability will be assessed by the clinician and by the clinical exam at the screening evaluation based on the clinician estimate of the disease trajectory during the 3 months pre-randomization). Subjects who meet the response criteria at 6 months will continue therapy for another 6 months. If in the subject's best interest, efforts will be made to provide access to study drug on compassionate basis beyond the 12-month study endpoint.

Patients who discontinue therapy for any reason will be followed for up to 24 months after starting pomalidomide as described in Section **6.1.3**.

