#### 6.2.2.1 Response Criteria

Efficacy will be assessed using NIH consensus criteria measuring for therapeutic response in clinical trials for cGvHD:

- **CR** is defined as complete resolution in all of signs and symptoms at all affected organs or tissues.
- **PR** is defined as improvement in ≥ 1 organ or tissue with no progression in any other affected organ or tissue. The calculations for PR and progressive disease (PD) are provided in Appendix H and Appendix I.
- **Response** < **PR** is defined as change towards improvement from the pre-treatment baseline but not meeting the criteria for CR or PR.
- **Stable Disease** is defined as no change in cGvHD, SD will be considered as response in patients with documented cGvHD progression over preceding 3 months.
- **Flare** is defined as exacerbation of cGvHD manifestations during withdrawal of immunosuppressive therapy which do not exceed those at the beginning of the trial and improves after reinstatement of previous treatment.
- **Progressive disease** is defined as failure of therapy to control cGvHD. The calculations for progressive disease (PD) are provided in Appendix I. Assessment by Organ-Specific Criteria. Patients who progress prior to 6 months evaluation will be also evaluable for the primary efficacy endpoint.
- **Mixed response** (improvement in some organs but worsening in others) will be categorized as progressive disease.

As outlined in Section **3.5**, type of involved organ, location and its measurements will be recorded at scheduled evaluations and reported on the appropriate CRF, equal to "Chronic GVHD Assessment (Clinician) Form," (Appendix G). All other measurements not being included in primary assessment but clinically related to cGvHD (e.g., change of pigmentation) will be reported in the source documents.

Skin and skin appendages: Skin assessments include 4 anatomic level of skin involvement:

- (1) erythematous rash (epidermal),
- (2) movable sclerosis (dermal),
- (3) non-moveable sclerosis, hidebound skin, or involvement of subcutaneous tissue and fascia (subcutaneous) and
- (4) ulceration (full thickness loss of epidermal tissue).

The first 3 measurements should be taken separately and recorded in metric notation using a body surface area (BSA). A cutaneous assessment worksheet for recording the BSA is provided (Appendix J). The size of ulcer should be measured the longest diameter (LD) of the largest ulcer.

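### Section 10's 90% power holds for a fixed 16-patient arm; with the mandatory 0-of-7 futility stop it is 85.6% to 90.1%, depending on overrun, and no operating characteristics are given for the stop

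*Combined protocol and SAP*

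**What the plan says.** Section 10 describes each arm as a single-stage design and states that, with 16 patients per arm, "an exact binomial test would have 90% power to detect a difference between a 5% response rate and a 30% response rate", at a one-sided 0.10 level. Three or more responses in 16 count as success. The selection probabilities that follow (93% and 84%) illustrate a rule that applies "if both arms are able to accrue to the full 16 patients", so the section itself foresees that an arm may not get there.

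The reason it may not is the futility rule in the same section: "if after 7 patients have enrolled on either arm, 0 have responded, then no further patients will be accrued to that arm". The rule is worded as mandatory, and it allows overrun: "patients may continue to be accrued beyond 7 in an arm, but no more patients would be registered and treated on that arm", with the stop taking effect "once the first 7 were evaluated and no PRs or CRs were identified in those first 7".

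The efficacy outcome is wider than that last phrase. Section 3.1 begins: "Efficacy outcome is defined as clinical response (CR or PR) in subjects who enter the study with stable cGvHD". For patients progressing at entry it goes on to accept stable disease of at least 3 months, and Section 6.2.2.1 agrees: "SD will be considered as response in patients with documented cGvHD progression over preceding 3 months". The primary evaluation is at 6 months (Sections 3.1 and 6.2.2), with response assessed every 3 months. Section 10 does not say at which assessment the first 7 patients are judged.

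Section 10 gives no probability of triggering the stop, no power or type I error with the stop in force, no expected sample size and no limit on overrun.

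**The concern.** A mandatory stop can only remove successes. An arm with no response in its first 7 patients could still have reached 3 responses among the other 9, and the fixed-sample calculation counts those paths as successes. Quoted without qualification beside the stop, 90% is the top of the range that the design can deliver.

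At stake is what a reader takes from Section 10. The chance of missing an arm with a true 30% rate could be up to 14.4% (100% − 85.6%) instead of about 10%. The reader also cannot see how often the rule would close an active or an inactive arm, although the second figure speaks in the design's favour.

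**Working it through.** **Inputs (Section 10).** n = 16 per arm; rates 5% and 30%; one-sided 0.10; success at 3 or more responses; stop if 0 of the first 7 respond. Number enrolled at the look: not stated, so it is varied as m = 7 to 16.

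**1. The plan's own figure.** P(X ≥ 3 | 16, 0.30) = 0.9006 and P(X ≥ 3 | 16, 0.05) = 0.0429. A cut-off of 2 would give alpha 0.189, so 3 is the smallest cut-off that meets 0.10. The stated 90% is reproduced.

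**2. Trigger probability**, assuming that the look uses the endpoint's definition and time point. At 30%: 0.7^7 = 0.0824. At 5%: 0.95^7 = 0.6983.

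**3. Power with the stop and no credit for overrun.** The lost paths are 0 of 7 followed by 3 or more of the remaining 9: 0.08235 × P(Bin(9, 0.3) ≥ 3) = 0.08235 × 0.53717 = 0.0442. Power = 0.9006 − 0.0442 = 0.8564. At a 5% rate the same step removes 0.0058, so alpha = 0.0429 − 0.0058 = 0.0371.

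**4. Power when overrun responses count.** If m patients are enrolled when the stop takes effect, and 3 responses are required whatever m is, power = 0.8564 + 0.08235 × P(Bin(m − 7, 0.3) ≥ 3).

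| Enrolled at look (m) | Power at 30% | Loss (points) | Alpha at 5% |
|---|---|---|---|
| 9 or fewer | 85.6% | 4.4 | 3.7% |
| 10 | 85.9% | 4.2 | 3.7% |
| 12 | 87.0% | 3.1 | 3.8% |
| 13 | 87.7% | 2.3 | 3.9% |
| 14 | 88.5% | 1.5 | 4.0% |
| 16 | 90.1% | 0 | 4.3% |

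**5. Sensitivity to the cut-off in a stopped arm.** Section 10 gives the cut-off of 3 only for n = 16. If the exact 0.10 test were applied at the n actually reached, the cut-off would be 2 for n up to 10. Power would then be 0.8564 + 0.08235 × 0.3^2 = 86.4% at m = 9, and 0.8564 + 0.08235 × P(Bin(3, 0.3) ≥ 2) = 0.8564 + 0.08235 × 0.216 = 87.4% at m = 10. Both lie inside the range in step 4.

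**6. Expected patients per arm**, from m × t + 16 × (1 − t) with t the trigger probability. With no overrun: 9.7 at a true 5% rate and 15.3 at 30%. With m = 12: 13.2 and 15.7.

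**7. Definition of the look.** Suppose the look counts only PR and CR, while the final test also counts stable disease in patients progressing at entry. A patient who responds only through stable disease then does not prevent the stop but does count at the end. At a matching time point this raises the trigger probability above 8.2% and lowers power at every m below 16; at m = 16 the stop removes nothing. A difference in time point could work the other way, if the look credited an early PR that is gone by 6 months.

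**The case against.** The strongest reply is that the sentence is right as written. It is conditioned on 16 patients per arm and follows directly on the words about a single-stage design. That stands: a reader might infer a calculation error, and there is none. What remains is that the section then adds a rule under which an arm may not reach 16, without saying that the 90% sets this rule aside.

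The second reply is that overrun may be large, because accrual continues until 7 patients have been evaluated and the endpoint is at 6 months. That also stands as a possibility. Section 2.1.3 says that the main recruitment source enrols about 3 persons per month, but that is the source's rate and not this trial's. As an illustration only, take a 6-month look, equal allocation, and 1, 2 or 3 patients randomised per month in total. Overrun is then 3, 6 or 9 per arm, and power is 85.9%, 87.7% or 90.1% if those responses count. A reader might infer that the true power is 86%. The documents do not support that either: it is one end of a range.

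Third, the case without credit for overrun has little textual support. Section 10 plans confidence limits around each arm's observed response proportion and does not exclude patients beyond the first 7. This is fair, but the section does not say how a stopped arm is judged, or against what cut-off.

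Fourth, the difference in definition is less firm than it looks. The rule itself speaks of patients who have responded, which under Section 6.2.2.1 can include stable disease; only the explanatory sentence narrows it to PRs and CRs. That is a reason to reconcile the passages, not to assume either reading.

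**Conclusion.** The point holds as an incomplete power statement. The 90% is correct for a fixed 16-patient arm. With the stop enforced, power per arm at a true 30% rate is 85.6% to 90.1%, with alpha 3.7% to 4.3% against the permitted 10%. The rule triggers with probability 8.2% at 30% and 69.8% at 5%. These figures assume that the look and the endpoint share response definition and time point; the intermediate values in the table also assume that 3 responses are needed at any n. The documents do not state the overrun, so they fix the loss only to between 0 and 4.4 points.

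Two stronger conclusions do not follow. A reader might infer that the trial is too small or the futility rule unsuitable. A loss of at most 4.4 points, with alpha well inside its limit, does not show that. A reader might also infer power near 80% from the stable-disease difference. That would need, for example, a fifth of responders to have stable disease only (trigger probability (1 − 0.24)^7 = 14.6%, power 80.3% without credit for overrun). The documents give no such share, so the figure is illustration only. What they support is the direction.

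**What to change.** Change the text of Section 10 only.

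- State that the 90% is the power for a fixed 16 patients per arm and excludes the futility stop.
- Add the operating characteristics as a range, for example:

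> With the 0-of-7 rule enforced, and the look using the endpoint's response definition and time point, power per arm at a true 30% rate lies between 85.6% and 90.1% (exact one-sided alpha 3.7% to 4.3%), depending on how many patients are enrolled at the look and whether their responses count. The rule is triggered with probability 8% at a true 30% rate and 70% at a true 5% rate.

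- State whether responses from patients enrolled beyond the first 7 count in a stopped arm, and against what cut-off.
- Reconcile the look's response definition and time point with Sections 3.1 and 6.2.2.1 before the figures are finalised. If they stay different, recompute under a stated assumption.

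The cost is a slightly less favourable power statement. No patients are added, and the sample size, the 3-of-16 cut-off and the 0-of-7 threshold stay as written.
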